8.3.5. Central Corneal Thickness

Central corneal thickness measurements of each eye will be made using an ultrasonic pachymeter. Contact pachymetry will be performed after IOP measurement.

8.3.6. Slit Lamp Biomicroscopy

A biomicroscopy examination will be performed without pupil dilation using a slit lamp and magnification consistent with standard clinical practice. The exam will include evaluation of patients' lids, cornea, conjunctiva, anterior chamber, and iris/pupils.

Screening will include a gonioscope to assess the angle closure. At Screening and EOS/ET, a lens assessment will be collected through a dilated pupil using the slit lamp biomicroscope. Findings will be evaluated for the presence and severity of nuclear, cortical, and posterior subcapsular lens opacities.

8.3.7. Dilated (Fundus) Exam

Stereoscopic fundus examination will be performed through a dilated pupil. The examinations will include evaluation of the macula, vitreous, and retina. The cup/disc ratio and presence of optic disc pathology will be determined using stereoscopic evaluation.

8.3.8. Visual Fields

Visual field examinations will be assessed using automated threshold visual field (using either 24-2 Swedish Interactive Thresholding Algorithm [SITA] standard, or Octopus G1 or 24-2 and dynamic or normal strategy). The same test methodology must be used throughout the entire study for a given patient. Visual fields must be reliable, defined as:

- Fixation losses $\leq 33\%$
- False positives $\leq 33\%$
- False negatives $\leq 33\%$

The gaze track and blind spot should be turned on in order to calculate the fixation losses. Visual fields should be performed with a non-dilated pupil, unless, in the opinion of the Investigator, the pupil is so miotic that dilation is required.

If a patient has prior results (within 3 months of Screening), these results can be used for entry if it meets the automated threshold visual field and considered reliable, otherwise it should be performed at screening to determine eligibility.

Testing can be performed at any point during a visit but *must be* performed prior to assessments requiring dilation.

8.3.9. Ocular Comfort Assessment PRO

Interviewer administered Ocular Comfort Assessment in the form of a PRO (see Section 15) is a snapshot of patient's ocular comfort (in both eyes) at the moment of administration. Patients should be educated on how to appropriately rate their level of ocular comfort on the scale at the Day 1 visit prior to the first administration of the PRO. This education should be repeated as needed at the investigators / PRO interviewers' discretion. However, great care must be taken to not unduly influence the outcome.

Prior to study treatment instillation (pre-dose), the PRO should be administered to assess the patient's current ocular comfort level.

Post-dose the PRO is to assess the ocular comfort in relation to drop instillation.

The PRO will only be administered during the AM dosing on Days 1, 7 and 14.

Trained site staff will administer the PRO pre-dose, immediately after drop instillation up to 2 minutes after instillation, 5 minutes (± 2 minute) and 10 minutes (± 5 minutes). If at the 10-minute time point the patient's comfort has not returned to that day's pre-dose value, the PRO should be administered every 30 minutes until the pre-dose value is achieved. The same trained interviewer should administer the PRO for a patient throughout a visit.

Investigator may use their discretion to perform ophthalmic assessments in addition to the PRO should the discomfort be persistent. Investigators should assess for adverse events if a patient's PRO values represent a grade change of 2 or more from that day's pre-dose values.

9. SAFETY

The methods for collecting safety data are described below.

9.1. Adverse Event (AE)

An AE is any untoward medical occurrence in a patient, which does not necessarily have a causal relationship with the study drug. An AE can therefore be any unfavorable and unintended sign, symptom, or disease temporally associated with the use of the study drug, whether or not considered related to the medicinal product. In clinical studies, an AE can include an undesirable medical condition occurring at any time, including baseline or wash-out periods, even if no study treatment has been administered.

Adverse events may be reported, spontaneously by the patient and/or,

- In response to an open question from the study personnel or revealed by observation will be recorded during the study at the investigational site.
- Lab abnormalities or changes from baseline that the Investigator deems as clinically significant
- Changes from baseline in study assessments that the Investigator deems clinically significant (i.e., blood pressure, pulse, etc.,)
- Abnormal values that constitute an SAE or lead to discontinuation of administration of Study treatment

The Investigator will assess the severity, causality (relationship to study drug), and seriousness of each AE.

9.1.1. Severity

The Investigator will assess the severity of all AEs as mild, moderate, or severe, based on the following definitions, developed from the Clinical Data Interchange Standards Consortium Study Data Tabulation Model standard terminology v3.1.1.

- **Mild:** A type of AE that is usually transient and may require only minimal treatment or therapeutic intervention. The event does not generally interfere with usual activities of daily living.
- **Moderate:** A type of AE that is usually alleviated with additional specific therapeutic intervention. The event interferes with usual activities of daily living, causing discomfort, but poses no significant or permanent risk of harm to the research patient.
- **Severe:** A type of AE that interrupts usual activities of daily living, or significantly affects clinical status, or may require intensive therapeutic intervention.

9.1.2. Relationship to Study Treatment

An Investigator who is qualified in medicine must make the determination of relationship to the study treatment for each AE (Unrelated, Possibly Related or Probably Related). The Investigator should decide whether, in his or her medical judgment, there is a reasonable possibility that the event may have been caused by the study treatment. If no valid reason exists for suggesting a

relationship, then the AE should be classified as “unrelated.” If there is any valid reason, even if undetermined, for suspecting a possible cause-and-effect relationship between the study treatment and the occurrence of the AE, then the AE should be considered “related.”

If the relationship between the AE/SAE and the study treatment is determined to be “possible” or “probable” the event will be related to the study treatment for the purposes of expedited regulatory reporting.

9.2. Recording/Reporting of Adverse Events

At each visit, the Investigator will elicit information on AEs. Any information on AEs should be recorded in the source documentation and in the electronic Case Report Form (eCRF). All clearly related signs, symptoms, and abnormal diagnostic procedures results should be recorded under one diagnosis.

The AE term should be reported in standard medical terminology. All AEs will be recorded by the date when the AE started and stopped, the severity, causality, seriousness, the action taken regarding SBI-100 Ophthalmic Emulsion, outcome and whether or not it caused the patient to discontinue the study.

For new ocular AEs, the Investigator must perform the appropriate ophthalmic procedures as needed to assess the affected eye. The Investigator will complete the associated eCRF page.

It is important to distinguish between serious and severe AEs. Severity is a measure of intensity whereas seriousness is defined by the criteria under [9.3](#). An AE of severe intensity may not be considered serious.

9.2.1. Reporting Period

The study period during which AEs must be reported is defined as the period from randomization to treatment until the EOS/ET visit, whether or not they are related to the study or study procedures, and they must be recorded in source document and EDC.

AEs that occur from the time of informed consent up until randomization to treatment will be assessed in accordance with the site processes and will be considered changes in patient health status. These events will be captured in the patients’ medical histories.

9.2.2. Timing, Treatment and Follow-up of AEs

During the study, AEs will be followed up until they have returned to baseline status, resolved and/or considered stabilized.

If an AE is not resolved at the time of the last visit, efforts will be made to follow up until resolution or stabilization of the event, unless the Investigator and Sponsor agree that follow-up is no longer necessary. Associated documentation of the follow-up and discussions on the handling of the AE should be available within the site files.

Treatment of AEs is at the discretion of the Investigator and should follow the standards of medical care at the Investigator’s institution.

9.3. Serious Adverse Events (SAE)

A serious adverse event is an AE occurring during any study phase (i.e., wash-out, treatment, or follow-up) that fulfills one or more of the following:

- Results in death
- It is immediately life-threatening: An AE is considered “life-threatening” if, in the view of either the Investigator or Sponsor, its occurrence places the patient at immediate risk of death. It does not include an AE that, had it occurred in a more severe form, might have caused death.
- It requires in-patient hospitalization or prolongation of existing hospitalization
- It results in persistent or significant disability or incapacity
- Results in a congenital abnormality or birth defect
- It is an important medical event that may jeopardize the patient or may require medical intervention to prevent one of the outcomes listed above.

9.3.1. Recording Serious Adverse Events

All SAEs (related and unrelated) will be recorded from the signing of the ICF until the EOS/ET visit. Any SAEs considered possibly or probably related to the study treatment and discovered by the Investigator at any time after the study should be reported.

All reports of congenital abnormalities/birth defects are SAEs. Spontaneous miscarriages should also be reported as SAEs as well as elective abortions without complications.

Note: Pre-planned surgeries or procedures for pre-existing known medical conditions for which the patient requires hospitalizations is not considered a SAE, if this was known at the time of screening.

9.3.2. Suspected Unexpected Serious Adverse Reaction (SUSAR)

Suspected Unexpected Serious Adverse Reaction (SUSAR) is the term used to refer to an AE that occurs in a clinical trial patient, which is assessed by the Sponsor and/or Investigator as being unexpected, serious, and having reasonable possibility of causal relationship with the study treatment.

Should an Investigator become aware of a patient experiencing a SUSAR during the study and at any time after the study, the Investigator/designee must report this to the Sponsor in the same manner as an SAE.

9.4. Reporting and Handling of Safety Events

9.4.1. Investigator Reporting: SAEs/SUSARs

All SAEs must be reported to the Sponsor/designee within 24 hours of the Investigator’s first awareness of the event. The Investigator/designee must:

- Enter all details into the AE CRF page ensuring that “serious” is noted

- Update any corresponding CRF pages with relevant information such as concomitant medications or procedures
- Compile all available and relevant medical records in support of the SAE, ensuring all personal health information has been redacted
- Complete an SAE Cover Letter with the Investigator's signature
- Email the entire packet to: [contact]

The Investigator will keep a copy of the SAE cover letter on file at the study site.

The Investigator will provide any additional information regarding the event to [contact] as soon as possible.

9.4.2. Investigator Reporting: Institutional Review Board (IRB)/Independent Ethics Committee (IEC) Notification

The Investigator is responsible for notifying the IRB/IEC of all SAEs that have occurred. All AEs that are study treatment related, serious, and unexpected (not listed in the IB) must be reported to the governing IRB/IEC as required by local regulations.

Copies of each report and documentation of IRB/IEC notification and receipt will be kept in the Investigator's study file.

9.4.3. Sponsor Reporting: Notifying Regulatory Authorities

The Sponsor is required to report certain study events in an expedited manner to the applicable Regulatory Agency as required by local regulations and/or governing health authorities. The following describes the safety reporting requirements of the FDA by timeline for reporting and associated type of event:

- Immediately and within 7 calendar days
 - Any suspected adverse reaction that is: associated with the use of the study treatment, unexpected, and fatal or life-threatening
 - Follow-up information must be reported in the following 8 calendar days
- Immediately and within 15 calendar days
 - Any suspected adverse reaction that is: associated with the use of the study treatment, unexpected, and serious, but not fatal or life-threatening
 - Any finding from tests in laboratory animals that suggest a significant risk for human patients including reports of mutagenicity, teratogenicity, or carcinogenicity
 - Any event in connection with the conduct of the study or the development of the investigational medicinal product that may affect the safety of the study patients
 - Follow-up information must be reported within 15 calendar days

For the purposes of expedited reporting, the determination of causality will be the responsibility of the Sponsor with consideration of the Investigator's assessment of causality.

The Sponsor will comply with all additional local safety reporting requirements, as applicable.

9.4.4. Sponsor Reporting: Notifying Participating Investigators

It is the responsibility of the Sponsor or designee to immediately notify all participating Investigators of any AE associated with the use of the drug that is both serious and unexpected, as well as any finding from tests in laboratory animals that suggest a significant risk for human patients.

9.5. Pregnancy

The definition of childbearing potential and approved methods of contraception are noted in [5.2.2](#).

Female patients must be advised to immediately inform the Investigator if she becomes pregnant during the study and must not receive further study treatment. Pregnancies occurring through the EOS/ET must be reported to the Investigator and recorded on a Pregnancy Report Form.

The Investigator must report all pregnancies to the Sponsor within 24 hours of notification. The Investigator should counsel the patient on the risks of continuing with the pregnancy and the possible effects on the fetus. Monitoring of the patient should continue until conclusion of the pregnancy.

If a female partner of a male patient becomes pregnant during the study, the Investigator will notify the Sponsor once the pregnancy is confirmed. The Investigator will obtain consent from the female partner to conduct safety follow-up assessments until the pregnancy has come to term. The outcome of the pregnancy should be documented.

Pregnancy is not considered an AE, unless there are pregnancy complications that may or may not be related to the study treatment.

At the completion of the pregnancy, the Investigator will document the outcome of the pregnancy.

The outcome of all pregnancies (spontaneous miscarriage, elective termination, normal birth, or congenital abnormality) must be followed up and documented even if the patient was discontinued from the study.

10. STATISTICS

10.1. Determination of Sample Size

From prior studies, the expected standard deviation (SD) of diurnal IOP in each treatment group ranges from 2.0 to 3.0 mmHg, with an average of 2.7 mmHg. The following estimates rely on a conservative SD of 3.0 mmHg for all visits and time points.

Analyses will be performed using a 2-sided alpha level of 0.05 for each test. For this feasibility study, no adjustments will be made for multiple comparisons across the multiple treatment groups versus the control group, or across tests for multiple visits and time points.

Sample sizes for both 80% and 90% power, and assuming a pooled SD of 3.0, are shown. The table below summarizes the sample size requirements for various expected differences in mean diurnal IOP between the active treatments and placebo. Sample sizes are shown prior to considering dropouts or non-compliance for the various endpoints and assumptions.

Table 5: Sample Size Requirements

Endpoint: Superiority of treatment over placebo for change from baseline (Day-1) at Day 14; SD = 3.0		
	Power	
	80%	90%
Difference (SBI-100 – Placebo) = 3.0	17	23
Difference (SBI-100 – Placebo) = 3.5	13	17
Difference (SBI-100 – Placebo) = 4.0	10	13

For this feasibility study, a difference of 3.0 mmHg in mean diurnal IOP between treatment and placebo is assumed with 80% study power.

Accounting for up to 5% dropout over a short-term study, an additional ~5% will need to be enrolled in each treatment group. For an expected difference of 3.0 mmHg at 80% power, $17/95\% = 18$ patients per treatment group will need to be enrolled, for a total of 54 patients in this 3-treatment group study.

10.2. Interim Analysis

There will be one interim analysis conducted when at least 50% treated patients have diurnal IOP measurement at 14 days post-dosing to assess the conditional study power. This interim analysis is not to stop the study for either efficacy or futility.

Conditional power will be calculated based on Brownian Motion Method illustrated by [Proschan, Lan and Witzes \(2006\)](#).

The conditional power for a two-sided test at level α (or one-sided test at level $\alpha/2$) under empirical treatment effect and standard deviation is defined as follows:

$$CP_\theta(t) = 1 - \phi\left(\frac{Z_{\alpha/2} - E_\theta\{B(1)|B(t)=b\}}{\sqrt{1-t}}\right),$$

Where θ and t represent the drift parameter and the information fraction, respectively, $E_\theta\{B(1)|B(t)=b\}$ denotes expected B value given $B(t)=b$, the expected B value is the drift parameter θ under empirical condition. The b value is expected B value under the null hypothesis

the drift parameter $\theta = 0$. The process to calculate conditional power will be described in the SAP.

10.3. Analysis Populations

10.3.1. Intent-to-Treat Population (ITT)

The Intent-to-Treat (ITT) population is defined as all patients who are randomized. The ITT population will be used for efficacy endpoints. Patients will be analyzed based on the treatment to which they were randomized.

10.3.2. Per Protocol Population

The Per Protocol population is a subset of the ITT population, defined as all patients who are randomized and do not have any major protocol deviations that could have an impact on study outcomes. Major protocol deviations will be defined in a masked review prior to study unmasking. Patients will be analyzed according to their actual treatment received. The Per Protocol population will be used for sensitivity analysis of the primary efficacy endpoints in the case of a significant number of major protocol deviations.

10.3.3. Safety Population

The safety population includes all patients randomized who received at least one treatment. Patients will be analyzed according to their actual treatment received. The safety population will be used for all safety analysis.

Additional analysis populations may be specified in the Statistical Analysis Plan (SAP).

10.4. Statistical Analyses

This section provides a broad outline of planned statistical summaries and analyses. Full details will be provided in a separate SAP for this study. Any changes to the data analysis methods described in the protocol will require an amendment only if it changes a principal feature of the protocol. Any other change to the data analysis methods described in the protocol, and the justification for making the change, will be described in the SAP.

10.4.1. General Considerations

Descriptive summary statistics will be provided for demographics and other baseline characteristics, disposition, and dose exposure. The number and percentage of patients who discontinued from the study, along with reasons for discontinuations, will be tabulated and described in listings.

Continuous data will be summarized using descriptive statistics (number of patients, mean, standard deviation, median, minimum, and maximum) and, where appropriate, graphic representation, and two-sided 95% confidence interval (CI); categorical data will be summarized by sample size and proportions.

Data summaries will be provided for the values at each scheduled visit, as well as changes from baseline at each scheduled visit. Baseline is defined as the last measure prior to the initiation of study treatment. For endpoints measured multiple times per day (e.g., IOP), there may be

multiple, time-specific baseline measures. Changes from baseline will use the time-specific baseline where applicable. For safety endpoints, data from unscheduled visits will be included in summaries of the worst-case post-baseline measure within each eye (for ocular data) or patient. Unscheduled visits will not be analyzed for efficacy endpoints.

The study eye will be determined for efficacy analysis purposes. The study eye will be defined as the eye with the highest mean diurnal IOP from the three measures taken on Day-1 (baseline). In the case of a tie, the study eye will be the right eye.

Unless otherwise specified, continuous variables will be analyzed using analysis of covariance (ANCOVA) at the two-sided 0.05 level at a visit. If data consists of multiple visits, mixed model with repeated measurement (MMRM) will be utilized. Categorical variables will be analyzed using the chi-square tests at the two-sided 0.05 level. Additional statistical methodology, sensitivity analyses accounting for missing data, and adjustments for covariates, if any, will be described in the SAP.

10.4.2. Primary Endpoint

The primary analysis will compare the change from baseline (Day-1) in mean diurnal IOP at Day 14 for each of the SBI-100 treatment groups to the placebo group. ANCOVA will be used for each comparison at a two-sided alpha level of 0.05 without any adjustment as described in [10.4.6](#). The model will include adjustment for the baseline value. The primary efficacy analysis will be based on the ITT population.

The null hypothesis for the primary endpoint is as follows:

The change from baseline (Day-1) in mean diurnal IOP of each dose level of SBI-100 Ophthalmic Emulsion will not be different from that of its placebo after 14 days of BID dosing.

For this feasibility study, the primary analysis will be based on observed data only, not imputing missing data. If the study eye is missing data on Day 14, the mean diurnal IOP will not be calculated for the primary analysis to avoid using a biased estimate. Thus, the while-on-treatment strategy for handling intercurrent events of early discontinuation will be employed.

The actual mean diurnal IOP values at each visit will be analyzed with MMRM.

Sensitivity analysis will be described *a priori* in the SAP and will include analyses on the Per Protocol population should there be a significant number of major protocol deviations. In the case of >5% of patients with missing data for any time point, the primary analyses will be repeated on the ITT population with imputed missing data (at the visit and time point level) following other intercurrent event strategies. Other methods for defining the study eye and analyzing both eyes in a random effects model may also be considered.

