15. Females of childbearing potential (not confirmed as post-menopausal or surgically sterile within the 6 months prior to screening) who are pregnant, nursing, or planning a pregnancy during the study and not using a reliable method of contraception from screening until at least 30 days after the last dose.
16. Males with partners of childbearing potential and do not agree to use a reliable method of contraception during the study and at least 30 days after the last dose.
17. Patients with a history of substance or alcohol abuse, considered chronic tetrahydrocannabinol (THC) users and/or test positive for alcohol or illicit drug use at Screening or Day-1.

Criteria for evaluation:

Efficacy:

- IOP measured by Goldmann applanation

Safety:

- Vital signs, safety labs, and adverse events (AEs) (overall, ocular, and non-ocular)
- Ophthalmic assessments: slit lamp biomicroscopy, dilated fundus exam, BCVA, pupil diameter, visual field and pachymetry
- Ocular comfort

Statistical Considerations:

With a sample size in each group of 18 including 5% attrition (total, n=54), the study will have 80% power to detect a difference of 3.0 mmHg or greater in mean diurnal IOP between each dose of active treatment and its placebo assuming a common standard deviation of 3.0 mmHg in diurnal IOP in each group, $\alpha = 0.05$ (two-sided). All statistical summaries and analyses will be performed using SAS software as detailed in the statistical analysis plan (SAP).

The primary analysis will compare the change from baseline (Day-1) in mean diurnal IOP at Day 14 for each of the SBI-100 treatment groups to the placebo group. Analysis of covariance (ANCOVA) will be used for each comparison, at a two-sided alpha level of 0.05. The model will include adjustment for the Day-1 value. The primary efficacy analysis will be based on

the Intent to Treat (ITT) population. The study eye will be defined as the eye with the highest mean diurnal IOP from the three measures on Day-1 (baseline). (In the case of a tie, the study eye will be the right eye).

For this feasibility study, the primary analysis will be based on observed data only, not imputing missing data. If the study eye is missing data for any time point on Day 14, the mean diurnal IOP will not be calculated for the primary analysis to avoid using a biased estimate. Thus, the while-on-treatment strategy for handling intercurrent events of early discontinuation will be employed.

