3. INVESTIGATIONAL PLAN

3.1. Overall Study Design

This is a multi-center, randomized, double-masked, placebo-controlled Phase 2 study to evaluate the ocular hypotensive efficacy, safety, and tolerability of SBI-100 Ophthalmic Emulsion after 7 days of binocular dosing, twice daily (BID).

The study will be conducted in 54 patients with elevated intraocular pressure at approximately 6 clinical research centers in the United States.

The study includes a 35-day screening period, which encompasses a wash-out (if needed), followed by a visit on Day-1 to confirm eligibility and provide baseline diurnal IOP, followed by a 14-day double-masked treatment period entailing topical BID dosing. The end of study (EOS) assessments will be performed within 2 days of the last dose on Day 14. Dosing will occur each day in the morning and in the evening 12 hours after the morning dose.

Study visits will occur on Days -35 to Day -2 (Screening), Day-1, Day 1, Day 7, Day 14, and (if not completed on Day 14) End of Study/Early Termination (EOS/ET).

At Screening, eligible patients will be asked to wash-out of their current IOP-lowering therapy (if currently using). Patients requiring wash-out will return for Day-1 at the completion of their wash-out, in accordance with the type of IOP-lowering therapy used. Patients who are treatment naïve may return upon confirmation of screening eligibility. On Day-1, diurnal IOP will be measured at 08:00 (± 30 m), 10:00 (± 30 m) and 16:00 (± 30 m) hours. If eligible, patients will be asked to return the following day to perform Day 1 procedures.

The first dose will occur in clinic on Day 1 with Investigation Product (IP) administered by the site staff in the morning immediately after the 08:00 IOP measurement and randomization via Interactive Response Technology (IRT). Subsequent study assessments up to 8 hours post-dose will be performed. The evening dose will be self-administered by the patient in the evening of Day 1 approximately 12 hours after the AM dose (~ 20:00) and continued for both mornings and evenings on Days 2 through 6.

Patients will return to the clinic on the morning of Days 7 and 14 for site administration of the morning dose with assessments up to 8 hours post-dose. The Day 7 evening dose will be self-administered by the patient in the evening approximately 12 hours after the AM dose (~ 20:00) and continued for both mornings and evenings on Days 8 through 13.

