Randomization			X						Via IRT after 08:00 IOP confirms eligibility
On-site Dosing			X		X		X		AM dose administered following 08:00 IOP. Treatment provided as a single use vial for binocular instillation BID. AM around 08:00 and PM around 20:00. Dose should be separated by 12 hours. Patient may self-administer PM dose on days 1 and 7.

	Visit 1	Visit 2	Visit 3	Visit 4	Visit 5	Visit 5a	
If not treatment naïve must wash-out of IOP-lowering therapy prior to Day-1.	Screening / Wash-out (D-35 to -2)	Day -1	Day 1		Day 7	Day 14	Day 14 – PM dose to occur on-site with EOS procedures following. Patient to self-administer PM dose if EOS procedures to occur on separate day. Procedures listed in EOS/ET are to be performed for any early terminations
Ocular Comfort PRO			S	S	S		Applies to AM dose occurring on-site. Pre-dose and immediately after drop instillation up to 2 mins, 5m±2m and 10m±5m post-dose. If at 10 min, PRO rating has not returned to the visit day pre-dose value, administer every 30 minutes until pre-dose value is achieved.
Kit Dispensing /Return			D	D/R	R	R	Day 1: patient education on drop instillation, handling, and storage. Return: used and un-used vials must be returned. Dispensing: discuss with the patient IP expectations and diversion prevention. Return: Staff must review with the patient vial level use and determine reasons for missed doses.
Prior/Concomitant Medications	X	X	X		X	X	
Adverse Events	X	X	X		X	X	Assessments performed outside of scheduled visits due to an adverse event should be captured as unscheduled visits.

H = hour (s), m = minute(s), S = serial procedures, D = Dispense, R = Return

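### The primary ANCOVA names only the Day -1 mean diurnal IOP as covariate, although a second pre-randomisation IOP (Day 1, 08:00) is collected in every randomised patient: a missed efficiency, not an error

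*Protocol*

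**What the plan says.** The primary analysis (protocol 10.4.2) is an ANCOVA of change from Day -1 to Day 14 in study-eye mean diurnal IOP, each dose against placebo. On covariates, 10.4.2 says "The model will include adjustment for the baseline value" and labels baseline as Day -1. The synopsis says "The model will include adjustment for the Day-1 value". Section 10.4.1 leaves any further covariate adjustment to the SAP.

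Inclusion criterion 3c requires an 08:00 IOP of 21 to 36 mmHg in each eye on both Day -1 and Day 1. The randomisation row of Table 2 reads "Via IRT after 08:00 IOP confirms eligibility", and section 3.1 places the first dose after that reading and after randomisation. So every properly randomised patient has a Day 1 08:00 IOP that treatment cannot have influenced.

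Section 10.4.1 also gives a general definition of baseline: the last value before treatment starts, time-specific where a measure is taken several times a day. For the 08:00 slot that is the Day 1 reading. For 10:00 and 16:00 it is Day -1.

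**The concern.** Mean diurnal IOP on Day -1 reflects the patient's stable pressure plus whatever was particular to that day. The same Day -1 readings choose the study eye (the one with the higher mean), and the 08:00 reading also screens the patient, so upward noise in them is favoured. A reading from another day, which plays no part in choosing the eye, helps separate stable pressure from one day's noise. Using it as a covariate should shrink the residual variance of the primary comparison at no cost in data collection.

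At stake is precision in a trial with 18 patients per arm, where a study eye missing any Day 14 time point drops out of the primary analysis. There is also an ambiguity to clear up. The 10.4.1 definition points to Day 1 for the 08:00 baseline, while 10.4.2 points to Day -1. Taken literally, 10.4.1 would make the secondary 08:00 change on Day 1 zero by construction.

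**Working it through.** **1. The plan's own figure.** Inputs from section 10.1: "Analyses will be performed using a 2-sided alpha level of 0.05 for each test"; "a difference of 3.0 mmHg in mean diurnal IOP between treatment and placebo is assumed with 80% study power"; "The following estimates rely on a conservative SD of 3.0 mmHg for all visits and time points"; "Accounting for up to 5% dropout over a short-term study". A two-sample t-test with n = 17 per group has noncentrality 3.0/(3.0 × √(2/17)) = 2.915 on 32 df and power 80.7%. With n = 16 it has 78.1%. So 17 is right, 17/0.95 = 17.9 gives 18 per group, and the same method reproduces all six cells of Table 5. With one covariate (31 df), power is 80.6%.

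**2. Share of residual variance removed.** Let X be the Day -1 mean of three readings, Z the Day 1 08:00 reading and Y the Day 14 mean of three readings. The share removed by adding Z is

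g = 1 − (1 − R²)/(1 − r_XY²), with R² = (r_XY² + r_ZY² − 2 r_XY r_ZY r_XZ)/(1 − r_XZ²).

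The documents give none of these correlations, so they are assumed through variance components.

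*Example, independent day effects:* patient 0.5, day 0.1, reading 0.4. Var(X) = 0.5 + 0.1 + 0.4/3 = 0.733; r_XY = 0.5/0.733 = 0.682; r_ZY = r_XZ = 0.5/√0.733 = 0.584; R² = 0.517; g = 1 − 0.483/0.535 = 9.8%.

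*Same components, with Day -1 and Day 1 day effects correlated 0.9:* r_XZ = 0.59/√0.733 = 0.689; R² = 0.490; g = 4.6%.

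Ranges over the settings tried:

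| Assumption | g |
|---|---|
| Independent day effects, full grid | 5.7% to 16.8% |
| As above, with the 21-36 mmHg limits on both days simulated | 6.0% to 12.5% |
| Day effects of the two adjacent days correlated 0.3 to 0.9 | 2.3% to 10.9% |

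Simulations that also pick the higher eye fall in much the same place: about 6% to 13% with independent day effects, with one set of components reaching 14.4%. With strongly shared day effects they give about 2% to 6%.

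**3. Power if 3.0 is the SD left after Day -1 adjustment.** SD = 3.0 × √(1 − g), n = 17, 31 df falling to 30:

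| g | 0 | 2% | 7% | 14% | 17% |
|---|---|---|---|---|---|
| Power | 80.6% | 81.3% | 83.3% | 86.0% | 87.2% |

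A g of 7% to 14% is worth about 1 to 2 of 17 patients per group (17 × 0.93 = 15.8; 17 × 0.86 = 14.6), or a confidence interval 4% to 7% narrower.

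**4. Power if 3.0 is the unadjusted SD.** The residual SD after Day -1 adjustment is 3.0 × √(1 − r_XY²):

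| r_XY | Residual SD | Power, Day -1 only | g = 7% | g = 14% |
|---|---|---|---|---|
| 0.5 | 2.60 | 90.3% | 92.2% | 94.0% |
| 0.6 | 2.40 | 94.2% | 95.5% | 96.7% |
| 0.7 | 2.14 | 97.7% | 98.4% | 98.9% |
| 0.8 | 1.80 | 99.7% | 99.8% | 99.9% |

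The larger values of g arise only with high r_XY, where power is already near its ceiling. Near r_XY = 0.5 to 0.6 the grid gives g of about 6% to 11%, which is a gain of about 1 to 2 points.

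**5. Cost of the extra covariate.** With k normally distributed covariates, chance imbalance inflates the variance of the treatment difference by 1 + k/(ν − 1), where ν is the residual df. For a two-arm fit of 34 patients, going from one covariate to two changes this from 1 + 1/30 to 1 + 2/29, a ratio of 1.034. For a three-arm fit of 51 it changes from 1 + 1/46 to 1 + 2/45, a ratio of 1.022. The covariate therefore pays for itself once g exceeds about 2% to 3%. The power figures in steps 3 and 4 charge only the lost degree of freedom, so they are slightly generous.

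**The case against.** The strongest reply is that nothing here is wrong. ANCOVA of change adjusted for the baseline of the same variable is standard and unbiased, it matches the endpoint, and the stated sample size is met without a second covariate. Section 10.4 describes itself as an outline, 10.4.1 leaves further covariates to the SAP, and saying that a model will include baseline does not exclude other terms. The study is also described as hypothesis-generating. All of this stands. It limits the point to the covariate that the protocol names, and to efficiency. It does not remove it, because the synopsis and 10.4.2 do specify the primary model, and those are the places where a better covariate set is most cleanly fixed.

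A reader might infer that choosing the study eye and screening on Day -1 readings biases the primary comparison. The documents do not support that. Both selections precede randomisation and act on all arms alike, and the Day 1 reading carries the same 21-36 mmHg limits, so it is itself truncated.

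A reader might also infer that the trial has under one point of power to spare and that this covariate would add three to six points. That holds only if 3.0 mmHg is already the residual SD after Day -1 adjustment. Section 10.1 introduces it as the SD of diurnal IOP in each group and calls it conservative against an average of 2.7; at 2.7, power is already 88%. Table 5 labels its endpoint as change from baseline, so the intended SD is not settled either way.

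**Conclusion.** The point holds as a missed efficiency. A valid second baseline exists in every randomised patient, and the protocol does not name it in the primary model. Whether the SAP adds it cannot be seen.

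The size is uncertain because every correlation is assumed. A range of about 2% to 17% of residual variance is defensible, and the answer depends mostly on how far Day -1 and Day 1, being consecutive, share day effects. If they share them strongly, the gain is close to the cost of the covariate. If they do not, there is a modest net gain. The effect on power runs from under one point to about six or seven if 3.0 mmHg is the adjusted SD, and is about 1 to 2 points from a higher start if it is unadjusted. The validity of the planned analysis is not in question.

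**What to change.** In the synopsis and 10.4.2, state that the primary ANCOVA includes two covariates, the Day -1 mean diurnal IOP and the Day 1 pre-dose 08:00 IOP of the study eye, or record why the second is not used. Keep change from Day -1 as the endpoint and the Day -1 rule for choosing the study eye.

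In 10.4.1, make the general baseline definition consistent with 10.4.2 by stating that the baseline for IOP change is Day -1 at every time point, including 08:00, and that the Day 1 08:00 reading enters only as a covariate. Make the change before unmasking and carry it into the SAP.

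The cost is a few lines of text and one degree of freedom. No additional measurement is needed.
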